2. TYPE OF PLANNED ANALYSIS

2.1. Final Analysis

Final Analysis includes the time period from the first date of OL TDF dose through and including the date of last OL TDF dose plus 30 days. As a result of early study termination (FPFV July 2015 to LPLV April 2018) only two patients completed 96 weeks of observation on TDF treatment for HBV, the primary study objective to characterize the safety profile (renal and bone adverse outcomes) of subjects will be summarized based on available TDF exposure time. The assessment of efficacy and tolerability of TDF will be described. As most of the enrolled subjects were unable to complete the target observation period of 96 weeks, the final analysis will be unable to provide meaningful evidence to suggest whether enhanced or standard of care renal and bone monitoring frequencies between Group 1 and Group 2 offer early detection and mitigation of renal or bone adverse events. Instead, the data will be described by monitoring group and pooled together where possible.

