3.1.3. Safety Analysis Set

The Safety Analysis Set includes subjects who were randomized into the study and received at least one dose of TDF. For this study there is no functional difference between FAS and the Safety Analysis Set.

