3.8.2. Analysis Windows

Subject visits might not occur on protocol-specified days. Therefore, for the purpose of analysis, observations will be assigned to analysis windows. Analysis windows will be calculated relative to study baseline.

Table 3-1. Windows of Time Relative to Study BL Used to Classify Subject Assessments (except DXA, Bone Biochemical Markers and Serology)

Period	Nominal Day	Lowest	Highest
Study BL ^a	1		1
Week 4	28	2	42
Week 12	84	43	126
Week 24	168	127	210
Week 36	252	211	294
Week 48	336	295	378
Week 60	420	379	462
Week 72	504	463	546
Week 84	588	547	630
Week 96	672	631	714
Follow-up Week 24		Last dose date + 155	Last dose date + 182

DXA, BMD, and serum bone biochemical markers data require special consideration, as they are collected infrequently, only at study BL and Weeks 24, 48, 72, and 96 (bone markers data are also collected at the screening visit). Randomization cannot occur until after the BL (pretreatment) DXA scan has been performed. As such, the windowing conventions depicted in [Table 3-2](#) will be used for DXA BMD data.

Table 3-2. DXA BMD and Bone Biochemical Markers Data Windows of Time Relative to Study BL Used to Classify Subject Assessments for Week 96 Analyses

Period	Nominal Day	Lowest	Highest
Study BL ^a	1		1
Week 24	168	2	252
Week 48	336	253	420
Week 72	504	421	588
Week 96	672	589	756

^a Study day computed from first dose date of TDF.

Windowing conventions to be used for serology data relative to study baseline are depicted in [Table 3-3](#).

Table 3-3. Serology Data Windows of Time Relative to Study BL Used to Classify Subject Assessments

Period	Nominal Day	Lowest	Highest
Study BL	1		1
Week 24	168	2	252
Week 48	336	253	420
Week 72	504	421	588
Week 96	672	589	756 *

a Study day computed from first dose date of TDF.

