7.2. Laboratory Evaluations

Selected laboratory data (using conventional units) will be summarized by the observed data and change over time. Missing laboratory results for safety summaries will not be imputed. In all cases for laboratory evaluations, no inferential statistics will be computed.

Glomerular filtration rate (estimated creatinine clearance) will be calculated via statistical programming at each visit

(a) using Schwartz formula for subjects ages 12–18 years (ie, 12 to < 19) as follows:

$$\text{Schwartz formula (mL/min/1.73 m}^2\text{)} = k \times L/\text{Scr}$$

k is a proportionality constant,

k=0.55 for adolescent females 12-18 years old; and

k=0.70 for adolescent males 12-18 years old

L is height in centimeters (cm); and

Scr is serum creatinine (mg/dL)

(b) using Cockcroft-Gault equation for age ≥ 12 years as follows:

$$\frac{(140 - \text{age in years}) (\text{body weight [kg]})}{(72) (\text{serum creatinine [mg/dl]})}$$

[Note: multiply estimated rate by 0.85 for women; use actual body weight]

Creatinine clearance (CLcr) summaries will be provided by Schwartz and Cockcroft-Gault separately.

Summaries and data listings will use the Safety Analysis Set. For subjects who discontinue prior to the final week for the given analysis, all on-treatment laboratory data collected on or before the date of last dose + 7 days will be included in tabular summaries. Laboratory data prior to the first dose date of TDF will be included in data listings.

Summaries of laboratory data will be provided for the safety analysis set. No inferential statistics will be generated.

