7.2.2.1. Treatment-Emergent Laboratory Abnormalities

Treatment-emergent laboratory abnormalities are defined as values that increase at least one toxicity grade from baseline at any time post-baseline up to and including the date of last dose of TDF plus 30 days. If the relevant baseline laboratory data are missing, then any abnormality of at least Grade 1 will be considered treatment emergent.

Treatment-emergent laboratory abnormalities and Grade 3 or 4 treatment-emergent laboratory abnormalities by monitoring group and overall will be summarized based on the date of the abnormality. Abnormalities that occur prior to the first dose date of TDF or during follow-up will be included only in data listings.

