7.2.2.3. Summaries of Laboratory Abnormalities

The following summaries (number and percentage of subjects) of laboratory abnormalities will be provided by monitoring group (subjects categorized according to most severe abnormality grade), where applicable:

- Treatment-emergent laboratory abnormalities
- Treatment-emergent marked laboratory abnormalities

For all summaries of laboratory abnormalities, the denominator is the number of subjects with non-missing post-baseline values in the given study period. A listing of treatment-emergent Grade 3 or Grade 4 laboratory abnormalities will be provided.

Incidence of ALT flare and post-treatment exacerbation of hepatitis is defined as follows:

- Serum ALT $> 2 \times$ study BL and $> 10 \times$ ULN, with or without associated symptoms

OR

- Confirmed ALT elevation (defined as 1-grade shift [ie, increase] or $2 \times$ previous value) with confirmed changes outside of the normal range in other laboratory parameters suggestive of worsening hepatic function (total bilirubin ≥ 2 mg/dL above study BL, abnormal prothrombin time ≥ 2 seconds over BL or international normalized ratio [INR] ≥ 0.5 over BL, abnormal serum albumin ≥ 1 g/dL below BL or elevated serum lactate levels [if available], defined as $2 \times$ ULN).

Summaries (number and percentage of subjects) of treatment-emergent, on-treatment laboratory abnormalities will be provided by monitoring group and overall, with the following modifications for the creatinine summaries:

Confirmed (defined as 2 consecutive visits) increase in serum creatinine of 0.3 mg/dL above BL

Confirmed (defined as 2 consecutive visits) increase in serum creatinine of 0.5 mg/dL above BL.

A confirmed laboratory results is defined as either being present at 2 consecutive visits or at the last visit. If the first of 2 consecutive results is on-treatment and the second is off-treatment, then the result is considered confirmed.

For all summaries of laboratory abnormalities, the denominator is the number of subjects in the Safety Analysis Set.

Hepatic flares will be summarized by monitoring group and overall.

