19.3.2	Treatment-Emergent Adverse Events Related to TDF	Grade 3 or 4 Bone or Renal Adverse Events	SAS
19.4	Treatment-Emergent Adverse Events	Leading to Permanent TDF Discontinuation	SAS
19.5	Treatment-Emergent Adverse Events	Leading to Change in Dose or Temporary Interruption of TDF	SAS
19.6	Treatment-Emergent Renal Adverse Events – Clinical Management and Outcomes Summary		SAS
19.7	Treatment-Emergent Bone-related Adverse Events – Clinical Management and Outcomes Summary		SAS
19.8	Treatment-Emergent Bone-related Adverse Events – Oral supplement use summary		SAS
19.9	Treatment-Emergent Serious Adverse Events		SAS
19.10	Treatment-Emergent Serious Adverse Events Related to TDF		SAS
20	Treatment-Emergent Adverse Events Occurring with >= 5% Incidence in Any Monitoring Group		SAS

Table Number	Title	Title	Analysis Set
21.1	Calcium (mg/dL) and Change from Baseline		SAS
21.2	Phosphorus (mg/dL) and Change from Baseline		SAS
21.3.1	Creatinine (mg/dL) and Change from Baseline		SAS
21.3.2	Creatinine Clearance (mL/min/1.73m ²) and Change from Baseline	Based on Schwartz	SAS
21.3.3	Creatinine Clearance (mL/min) and Change from Baseline	Based on Cockcroft-Gault	SAS
22.1	N-telopeptides (nmol BCE/L) and Change from Baseline		SAS
22.2	C-telopeptides (ng/mL) and Change from Baseline		SAS
22.3	Serum Osteocalcin (ng/mL) and Change from Baseline		SAS
22.4	Bone-Specific Alkaline Phosphatase (µg/L) and Change from Baseline		SAS
22.5	Serum PTH (pg/mL) and Change from Baseline		SAS
22.6	Vitamin D Level (25-hydroxy) (ng/mL) and Change from Baseline		SAS
23.1	Treatment-Emergent	Laboratory Abnormalities by Grade	SAS
23.2	Treatment-Emergent	Laboratory Abnormalities	SAS
23.3	Treatment-Emergent	Grade 3 or Grade 4 Laboratory Abnormalities	SAS
23.4	Treatment-Emergent	Marked Laboratory Abnormalities	SAS
24	Hepatic and Renal Related Abnormalities	Treatment-Emergent	SAS
25	On-Treatment ALT Flare and post treatment Exacerbation of Hepatitis		SAS
26.1	Cumulative Incidence of At Least a 4% Decrease from Baseline in Spine Bone Mineral Density (g/cm ²) by Week		SAS
26.2	Percent Change from Baseline in Spine Bone Mineral Density (g/cm ²) by Week	Categorical Summaries	SAS
26.3	Z-Scores for Spine Bone Mineral Density (g/cm ²) and Change from Baseline by Week	Categorical Summaries	SAS

Table Number	Title	Title	Analysis Set
27.1	Cumulative Incidence of At Least a 4% Decrease from Baseline in Whole Body Bone Mineral Density (g/cm ²) by Week		SAS

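### SAP 7.2.2.3 gives two conflicting denominators for laboratory abnormalities, and no counting period is stated for post-treatment exacerbation in Table 25

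*SAP*

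**What the plan says.** SAP 7.2.2.3 sets the denominator for all laboratory-abnormality summaries twice. After the bullets naming the treatment-emergent and marked-abnormality summaries, it says that "the denominator is the number of subjects with non-missing post-baseline values in the given study period". Further down, after the creatinine confirmation rules and just before the hepatic-flare summary, it says: "For all summaries of laboratory abnormalities, the denominator is the number of subjects in the Safety Analysis Set". Neither sentence is limited to particular tables. Membership of that set requires no laboratory result (SAP 3.1.3): "The Safety Analysis Set includes subjects who were randomized into the study and received at least one dose of TDF".

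The same section gives one definition for ALT flare and post-treatment exacerbation of hepatitis. Appendix 3 lists a single Table 25, "On-Treatment ALT Flare and post treatment Exacerbation of Hepatitis", with SAS in the analysis-set column.

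On timing, SAP 1.2 follows subjects who stop TDF for 24 weeks off treatment or until active treatment starts. SAP 2.1 runs the final analysis "through and including the date of last OL TDF dose plus 30 days". SAP 7.2.2.1 adds: "Abnormalities that occur prior to the first dose date of TDF or during follow-up will be included only in data listings". SAP 7.2.2.3 gives no period over which a post-treatment exacerbation is to be counted.

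**The concern.** Two programmers could each follow the SAP and report different percentages from the same data. The choice also affects meaning. With the Safety Analysis Set as denominator, a subject who was never tested is indistinguishable from one who was tested and normal. The study exists to compare two testing schedules, so the number tested is likely to differ by group, and a common denominator can hide that.

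Table 25 raises a separate question. It is meant to report an outcome that occurs after TDF is stopped, while two general rules would keep late off-treatment results out of the tables. Protocol 7.5.7 notes that severe exacerbations after stopping HBV therapy have included deaths. A reader therefore needs to know whether a zero in that table means no events or no observation.

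**Working it through.** The plan states no figure to reproduce. The check compares the rules and adds simple proportions and day counts.

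**1. When the two denominators agree.** Let N be the Safety Analysis Set size, m the number with a non-missing post-baseline value for the test, and x the number with the abnormality. One rule reports x/m and the other x/N. Their ratio, (x/N)/(x/m) = m/N, is 1 only if m = N.

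Inputs: 30 enrolled, 15 per group (SAP 1.4). I assume all were dosed, so N = 15 per group. The documents do not give m, so the values below are assumed, with x = 1.

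| m (assumed) | x/m | x/N |
|---|---|---|
| 15 | 6.7% | 6.7% |
| 12 | 8.3% | 6.7% |
| 10 | 10.0% | 6.7% |
| 8 | 12.5% | 6.7% |
| 5 | 20.0% | 6.7% |

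**2. Why m may differ by group.** In the procedures table (Protocol Appendix 2, SAP Appendix 1), Group 1 has post-baseline renal chemistry at Week 4, Week 12 and every 12 weeks to Week 96. Group 2 has it only at Week 96, with local care otherwise. SAP 2.1 reports two completers, so 30 − 2 = 28 subjects did not complete 96 weeks.

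Early-discontinuation visits do not close the gap with certainty. Protocol 6.4.2 to 6.4.5 tie that visit to the assessments of the coming week, where renal chemistry is marked for Group 1. Protocol 6.4.6 ties it to the Week 96 list, which includes renal chemistry for both groups. Local testing may supply other values. SAP 3.9.1 itself cites ad hoc testing in Group 2 when choosing how to handle missing efficacy data.

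Illustration, one event per group, with 15 tested in Group 1 and an assumed 5 in Group 2: x/N gives 1/15 = 6.7% in both groups, while x/m gives 1/15 = 6.7% against 1/5 = 20.0%.

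**3. Counting period for post-treatment exacerbation.** Maximum follow-up is 24 × 7 = 168 days. If the SAP 2.1 limit governs Table 25, at most 30 of 168 days (17.9%) can contribute, and 168 − 30 = 138 days cannot. Subjects who start other HBV therapy sooner have less follow-up to lose.

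SAP 7.2.2.2 counts values up to last dose + 30 days as on-treatment for marked abnormalities. If that boundary were also used in Table 25, the post-treatment period would begin where the SAP 2.1 period ends, leaving nothing to count.

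The protocol does not settle the matter. Section 8.2.1.1 includes the treatment-free follow-up in safety summaries, 8.2.1.2 stops at 30 days after treatment, and 8.6 summarizes to the last dose and lists the rest.

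**The case against.** The best defence is that the two denominator sentences were meant for different tables: the first for the graded summaries listed just above it, the second for the creatinine and flare summaries around it. That is plausible, but both sentences claim all summaries and nothing assigns them.

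Several stronger readings are tempting and should be resisted:

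- *That the SAP has no off-treatment window.* Table 3-1 has a "Follow-up Week 24" window, from 155 to 182 days after the last dose. What is missing is a counting period for this outcome.
- *That Table 25 must use the Safety Analysis Set as denominator.* The Appendix 3 column names an analysis set. Tables 8.1, 11 and 13 are labelled FAS yet exclude missing values, so the label does not fix the denominator. Nor does a shared title rule out separate rows.
- *That subjects who switched therapy will be counted as events.* Off-treatment follow-up ends when active treatment starts (SAP 1.2), and Protocol 7.5.7.1 takes a subject who starts alternative therapy out of the study. ALT after a switch is generally outside planned follow-up.
- *That nearly all follow-up is lost to a 7-day limit.* SAP 7.2 says "all on-treatment laboratory data collected on or before the date of last dose + 7 days will be included in tabular summaries", which concerns on-treatment data and does not clearly govern a separately defined post-treatment outcome.

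The listings-only sentence also sits under treatment-emergent abnormalities, so its reach to Table 25 is arguable. SAP 7.2.2.3 does accept an off-treatment result to confirm an on-treatment one. The SAP 2.1 limit is general and remains the main obstacle.

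Two practical objections stand. The procedures table schedules no liver chemistry after Week 96, so off-treatment ALT may be sparse. And ALT above 10 × ULN is Grade 4, so Listing 17.2.1 can show it. However, the second route in the definition, a one-grade ALT rise with other hepatic changes, can be met below Grade 3 and need not appear there.

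**Conclusion.** The denominator conflict is certain, because both sentences are on the page and cannot both apply unless everyone was tested. That it can dilute the groups unequally follows from the renal schedule and the two completers. How far it does so depends on the number tested, which the documents do not give. If all 30 were dosed and tested, there is no effect.

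The timing point is conditional. No counting period is stated for post-treatment exacerbation, and a literal reading of SAP 2.1 and 7.2.2.1 can drop later events from Table 25.

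Severity is minor. SAP 7.2 rules out inferential statistics for laboratory data, SAP 2.1 already disclaims meaningful evidence on the monitoring comparison, and no primary conclusion changes. The percentages above are illustrations and not estimates.

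**What to change.** 1. In SAP 7.2.2.3, delete the Safety Analysis Set denominator sentence. Keep subjects with at least one non-missing post-baseline value for that test, and print that number per group.
2. In Table 25, report on-treatment flare and post-treatment exacerbation in separate rows, and state where the on-treatment period ends.
3. Count post-treatment exacerbation from all ALT after that point to 24 weeks or the start of other HBV therapy, whichever is first. State that this row is exempt from the +30-day and listings-only limits.
4. Use as its denominator subjects with at least one such ALT, and show the number untested beside it.

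The cost is one sentence deleted, a short window rule added, and one split row with counts in an existing descriptive table. No new data are needed. The downside is a small post-treatment denominator that may over-represent subjects tested for cause and so push the rate upward. The untested count lets the reader judge this.

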6.4.2. Group 1: Week 12 and 36 Assessments

Study Visit for Weeks 12 and 36 should be completed \pm 7 days of the protocol-specified visit date, based on the Baseline Visit. Group 2 subjects will follow local standard of care for renal monitoring and AE collection. The following assessments and procedures will be performed and recorded on CRFs:

- Complete physical examination including, vital signs, body weight and height
- Group 1: Urinalysis (protein, glucose, creatinine, phosphate, bicarbonate, blood, calcium), fasting required
- Blood samples for:
 - Group 1: Serum renal chemistry (creatinine, glucose, creatinine clearance (calculated), magnesium, bicarbonate, chloride, potassium, sodium), fasting required
 - Plasma HBV DNA (PCR method)
- Review of bone and renal AEs and any associated medical management
- Concomitant medications (including dietary supplements such as calcium, vitamin D, phosphorus)
- Assessment of medication adherence
- Tenofovir DF dispensing and instructions on appropriate dosing and administration

- Screening for pregnancy (urine screen)

Subjects who discontinue the study prior to the Week 12 or 36 Visit will complete all Week 12 or 36 assessments and procedures at an Early Drug Discontinuation Visit, to be completed within 72 hours of last dose of Tenofovir DF. Subjects who have received at least one dose of Tenofovir DF and permanently discontinue treatment will be followed for 24 weeks off treatment or up to initiation of an alternative treatment regimen, whichever occurs first.

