Appendix 2. Study Procedures Table

Study Procedures	Study Week												
	Screening	Baseline	4	12	24	36	48	60	72	84	96	30d Follow-Up	
Written Informed Consent	x												
Medical History	x												
HBV DNA		x		x	x	x	x	x	x	x	x		
HBV serology	x	x			x		x		x		x		
HCV, HDV, HIV testing		x											
HBV genotype		x											
DEXA, Group 1		x			x		x		x			x	
DEXA, Group 2		x					x					x	
Serum bone chemistry, Group 1		x			x		x		x			x	
Serum bone chemistry, Group 2		x					x					x	
Serum renal chemistry, Group 1	x	x	x	x	x	x	x	x	x	x	x	x	
Serum renal chemistry, Group 2*	x	x										x	
Liver chemistry	x	x			x		x		x			x	
Hematology		x			x		x		x			x	
Urinalysis, Group 1 (see * for Group 2)	x	x	x	x	x	x	x	x	x	x	x	x	
Complete physical examination	x	x		x	x	x	x	x	x	x	x	x	
Changes in medical status or symptoms, Group 1 (see † for Group 2)		x	x										
Drug dispensed and accountability/Concomitant medications		x	x	x	x	x	x	x	x	x	x	x	
Assess for AE, including renal and bone events (see † for Group 2)		x	x	x	x	x	x	x	x	x	x	x	x
Pregnancy test	x	x		x	x	x	x	x	x	x	x	x	

[figure not shown]
* Group 2 will follow local standard of care for renal monitoring, which may include the Tenofovir DF SmPC recommended screening intervals

† Group 2 subjects may have changes in medical status or symptoms and new AE assessed upon return for renal monitoring, as per standard of care and within the 12 week intervals of scheduled physical examinations

Definitions:

HBV serology	HBeAg, HBsAg, anti-Hbe, anti-HBs
Serum bone chemistry	calcium, phosphorus, 25-hydroxy and 1, 25 dihydroxyvitamin, PTH, osteocalcin, bone alkaline phosphatase, N and C telopeptides
Serum renal chemistry	glucose, creatinine, creatinine clearance (calculated), magnesium, bicarbonate, chloride, potassium, sodium
Liver chemistry	alanine aminotransferase (ALT), alkaline aminophosphatase (ALP), aspartate aminotransferase (AST), total and direct bilirubin, total protein, albumin, gamma glutamyl transpeptide (GGT), LDH, CK
Hematology	PT/INR, complete blood count (CBC) with differential, platelets
Urinalysis	glucose, protein, creatinine, phosphate, bicarbonate, blood, calcium
Complete physical exam	includes vital signs, body weight and height

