3.9. Handling Missing Data in Evaluation of Efficacy

3.9.1. Missing = Excluded Analysis

The primary method of handling missing data in evaluation of efficacy is the missing = excluded (M = E) approach. Due to the ad-hoc nature visits and tests within study group 2, M=E is preferred.

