Appendix 1. Study Procedures Table

Study Procedures	Screening	Baseline	Study Week									30d Follow-Up
			4	12	24	36	48	60	72	84	96	
Written Informed Consent	x											
Medical History	x											
HBV DNA		x		x	x	x	x	x	x	x	x	
HBV serology	x	x			x		x		x		x	
HCV, HDV, HIV screening		x										
HBV genotype		x										
DXA, Group 1		x			x		x		x		x	
DXA, Group 2		x					x				x	
Serum bone chemistry, Group 1		x			x		x		x		x	
Serum bone chemistry, Group 2		x					x				x	
Serum renal chemistry, Group 1	x	x	x	x	x	x	x	x	x	x	x	
Serum renal chemistry, Group 2*	x	x									x	
Liver chemistry	x	x			x		x		x		x	
Hematology		x			x		x		x		x	
Urinalysis, Group 1 (see * for Group 2)	x	x	x	x	x	x	x	x	x	x	x	
Complete physical examination, Groups 1 and 2	x	x		x	x	x	x	x	x	x	x	
Changes in medical status or symptoms, Group 1 (see † for Group 2)		x	x									

Study Procedures	Screening	Baseline	Study Week									30d Follow-Up
			4	12	24	36	48	60	72	84	96	
Drug dispensed (as required) and accountability/Concomitant medications		x	x	x	x	x	x	x	x	x	x	
Assess for AE, including renal and bone events (see f for Group 2)		x	x	x	x	x	x	x	x	x	x	x
Pregnancy test	x	x		x	x	x	x	x	x	x	x	

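### SAP 7.2.2.3 gives two conflicting denominators for laboratory abnormality percentages; the Safety Analysis Set version counts untested subjects as event-free, which for renal tests can favour Group 2

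*SAP*

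**What the plan says.** SAP 7.2.2.3 first lists the summaries of treatment-emergent and marked abnormalities. It then says, for all laboratory abnormality summaries, that "the denominator is the number of subjects with non-missing post-baseline values in the given study period". The ALT flare definition and the confirmed-creatinine rules follow. After them comes a second rule with the same opening: "For all summaries of laboratory abnormalities, the denominator is the number of subjects in the Safety Analysis Set".

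The surrounding rules are:

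- **Who is in the set.** SAP 3.1.3 requires randomization and one dose. No post-baseline laboratory value is needed.
- **Missing results.** SAP 7.2: "Missing laboratory results for safety summaries will not be imputed".
- **What counts as an event.** SAP 7.2.2.1 defines an abnormality by an observed rise of at least one grade after baseline.
- **Renal schedule.** Group 1 has renal chemistry at Weeks 4 and 12 and every 12 weeks after that (Protocol 3.2). In the SAP Appendix 1 row "Serum renal chemistry, Group 2", the only post-Baseline mark is at Week 96. The footnote to Protocol Appendix 2 says "Group 2 will follow local standard of care for renal monitoring, which may include the Tenofovir DF SmPC recommended screening intervals".
- **Efficacy, by contrast.** SAP 3.9.1 excludes missing values and gives the reason: "Due to the ad-hoc nature visits and tests within study group 2, M=E is preferred".

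**The concern.** Two rules that each claim to govern every table cannot both be followed once any subject lacks a result. The programmer's choice then sets the percentages in Tables 24 and 25 and, on a literal reading, in Tables 23.1 to 23.4 as well.

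The Safety Analysis Set rule is the troublesome one. A subject with no post-baseline result can never enter the numerator but stays in the denominator, and so is counted as having no abnormality. If the share tested differs between groups, the percentages differ even when the risk does not. Renal tests are where that share can differ, because the two monitoring groups are defined partly by how often renal function is tested. The classification of detected renal and bone laboratory abnormalities is a secondary endpoint (Protocol 8.1.3). SAP 2.1 falls back on description by monitoring group, so these percentages are themselves what will be reported.

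**Working it through.** The plan states no figure for this point, so there is nothing to reproduce. The check has three steps.

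**1. Do the rules differ?** Let N be the group size in the Safety Analysis Set, m the number with a post-baseline result, and r the proportion with an abnormality among those tested.

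- Tested rule: (r × m) / m = r.
- Safety Analysis Set rule: (r × m) / N = r × m/N.

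They agree only when m = N.

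**2. Can m/N differ by group?**

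- Group 1 has a required creatinine from Week 4. Group 2 has one scheduled only at Week 96, with local care in between.
- SAP 2.1 reports that only two subjects completed 96 weeks.
- The early-exit rules in Protocol 6.4.2 to 6.4.5 tie the exit visit to the upcoming visit's tests. For example, 6.4.2 says "Subjects who discontinue the study prior to the Week 12 or 36 Visit will complete all Week 12 or 36 assessments and procedures". The renal panels in those sections are labelled Group 1.
- Liver chemistry has the same 24-weekly schedule in both groups, so no comparable imbalance between groups is built in for ALT.

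**3. How large could the effect be?** Inputs:

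- N = 15 per group (SAP 1.4), assuming that all were treated.
- All 15 of Group 1 tested (assumption).
- 10 or 5 of Group 2 tested (assumption; the documents give no number).
- The same r in both groups. The value 4.5% is the paediatric renal toxicity figure in Protocol 8.9, an imperfect proxy for a graded laboratory change. The value 20% is an assumption with no source.

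The spurious gap under the Safety Analysis Set rule is r × (15 − m)/15, where m is the number tested in Group 2.

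| r | Group 2 tested | Group 1 shown | Group 2 shown | Gap (points) |
|---|---|---|---|---|
| 4.5% | 10 | 4.5% | 4.5% × 10/15 = 3.0% | 1.5 |
| 4.5% | 5 | 4.5% | 4.5% × 5/15 = 1.5% | 3.0 |
| 20% | 10 | 3/15 = 20.0% | 2/15 = 13.3% | 6.7 |
| 20% | 5 | 3/15 = 20.0% | 1/15 = 6.7% | 13.3 |

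Under the tested rule the gap is zero in every row; in the 20% rows Group 2 shows 2/10 or 1/5, both 20.0%. The 4.5% rows are expected values, not possible counts, since 0.045 × 15 = 0.675 of a subject.

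**The case against.** - **Placement.** The second sentence follows the flare and creatinine text and may have been meant only for those summaries. That is a fair reading, and on it Tables 23.1 to 23.4 have one denominator. The text nevertheless says all, and the narrower reading puts the rule on creatinine, where required testing differs by group.
- **Few may be untested.** Protocol 7.5.4 has creatinine clearance calculated at each visit, with no group limit. Protocol 6.4.6 can be read as requiring the Week 96 renal and liver tests at any early exit. It is also the only assessment list headed as the end-of-treatment visit, which Protocol 3.2 asks of everyone who stops the drug for good. Local care may follow the SmPC intervals. Protocol 7.5.7 asks for at least 6 months of hepatic monitoring after HBV therapy stops, although the schedule shows no liver panel at follow-up. All of this stands. It leaves the number untested unknown and possibly small. It does not remove the conflict, because 7.5.4 and 6.4.6 themselves sit uneasily with the Group 2 schedule and with 6.4.2 to 6.4.5.
- **Testing is already visible.** SAP 7.2.1 gives the sample size by group at each window, so extra per-week counts are not needed. The abnormality tables would still carry a misleading percentage.
- **Little hangs on it.** SAP 7.2 rules out inferential statistics for laboratory data. SAP 2.1 already says that the data cannot settle which monitoring frequency is better. Abnormalities that need intervention or a change in dosing are recorded as adverse events (Protocol 7.1.3). This is right, and it is why the point is minor.

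A reader might infer that Group 2's renal abnormalities will in fact be understated, or by as much as 13 points. The documents do not support that: they give neither the number tested nor a 20% risk. In the earlier adolescent CHB trial no subject had a confirmed creatinine rise of at least 0.5 mg/dL (Protocol 1.2.3.1).

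**Conclusion.** The conflict is certain and lies in the wording of SAP 7.2.2.3. It also follows directly from the SAP's own rules that the Safety Analysis Set denominator treats untested subjects as event-free. That this can favour Group 2 on renal tests is a possibility that the schedule permits, not a demonstrated bias. Its size rests on assumed numbers tested and assumed risks, and it is zero if every Group 2 subject has a post-baseline creatinine in the database. No test, error rate or primary result depends on it. It is a minor inconsistency, worth correcting because by-group description is all that this analysis will offer, and because the SAP takes the opposite approach for efficacy on account of irregular Group 2 testing.

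**What to change.** In SAP 7.2.2.3, delete the Safety Analysis Set sentence and reword the remaining one along these lines: *For each laboratory test, percentages are based on Safety Analysis Set subjects who have one or more recorded results for that test after baseline within the study period being summarised.* In Tables 23.1 to 23.4, 24 and 25, print number tested / number treated by monitoring group.

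The cost is one sentence removed, one reworded and one added row in six tables; no new data are needed. There is a downside: local tests in Group 2 may be ordered on suspicion, which can push a tested-only percentage upward. Printing the two counts together lets the reader see how selective testing was. The change does not cure under-detection from fewer tests per Group 2 subject, so any group difference in renal laboratory abnormalities should still be read with the testing frequency in mind.
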